13.5.2 Additional Short-term Efficacy Estimand

In addition to the short-term efficacy estimand described in section [13.5.1](#) the population level summary ‘mean change across weeks 1-2’ will be considered with everything else as described in section [13.5.1](#) except that the contrast used is [1, 1] [1, 2] /divisor = 2.

13.5.3 Long-term Efficacy Estimand

The long-term efficacy estimand is the mean change from Baseline in the monthly number of attacks (Months 1-12) for participants with chronic cluster headache receiving IV infusion of eptinezumab 400 mg every 12 weeks, without the use of transitional treatment (GON block and oral steroids), and with continuation of treatment eptinezumab 400 mg for 12 months, and regardless of use of abortive and preventive medication for cluster headache, and infusion interruption or termination before full dose is received.

The approach described in section 13.5.1 also apply for the long-term estimand with a few adjustments:

- The **clinical question of interest** is changes in cluster headache attacks within the 12 months after infusion with eptinezumab 400 mg.
- The **endpoint to be obtained to address the clinical question** is change from Baseline in the monthly number of attacks (Months 1-12)
- The **population level summary** will be the mean change across Months 1-12
- The **intercurrent events** use of transitional treatment and interruption or termination of IMP such that full dose is not received will be handled as in section 13.5.1. Furthermore, when the primary reason is either “Lack of Efficacy” or “Adverse Events” for withdrawal from treatment this will be considered an intercurrent event that will be handled by a hypothetical strategy

Intercurrent Events

In addition to the intercurrent events described above, the following intercurrent event, occurring after treatment initiation and potentially affecting either the interpretation or the existence of the measurements associated with the clinical question of interest, is considered.

- Withdrawal from treatment due to “Lack of Efficacy” or “Adverse events” –
Hypothetical strategy

For participants withdrawing from treatment, the majority of the effect is expected to be seen within the first 12 weeks following their last infusion and therefore data that occur beyond 12 weeks after their last infusion will not be considered.

Estimator

The intercurrent event withdrawal from treatment will be handled by a hypothetical strategy estimating the effect where all participants continue their treatment with eptinezumab 400 mg for 12 months by not including data collected 3 months or more after the latest infusion.

Furthermore, the following adjustments are needed compared to the estimator in section 13.5.1

- The week variable in the MMRM will be replaced by Month 1 to 12
- The DPS2 will be replaced by DPS3
- The contrast that will be used is given as [1, 1] [1, 2] [1, 3] [1, 4] [1, 5] [1, 6] [1, 7] [1, 8] [1, 9] [1, 10] [1, 11] [1, 12] /divisor = 12

13.5.4 Rationale for the Efficacy Endpoints following the strategy of the Long-term Efficacy Estimand

Regarding the efficacy endpoints based on the number of cluster headache attacks, intensity of pain or use of abortive medication, the data handling will follow the strategies described in section 13.5.3. For all of these endpoints, the intercurrent events use of transitional treatment

and interruption or termination of IMP such that full dose is not received and withdrawal from treatment will be handled as described in section [13.5.3](#).

For endpoints based on the number of attacks the rationale is the same as previously described. For endpoints based on intensity of pain the same strategies are used since not getting the full dose (by interruption/termination of IMP or withdrawal from treatment) is expected to also affect the pain as well as use of transitional treatment is expected to decrease the pain severity.¹ For endpoints based on the use of abortive medication, not getting the full dose (by interruption/termination of IMP or withdrawal from treatment) is expected to also affect the use of abortive medication. Furthermore, the use of transitional treatment is expected to reduce the number of attacks and therefore is also expected to reduce the number of times abortive medication can be used.

13.5.5 Intercurrent Events and Withdrawal from Treatment

The number of participants who experienced the intercurrent event “use of transitional treatment” and “interruption or termination of IMP such that full dose is not received” during Weeks 1-4 will be summarized for the short-term efficacy estimand defined in sections [13.5.1](#) and [13.5.2](#).

The number of participants who experienced the intercurrent events “use of transitional treatment”, “interruption or termination of IMP such that full dose is not received” and “withdrawal from treatment” during Months 1-12 will be summarized for the long-term efficacy estimand following the definition in section [13.5.3](#).

The number of participants who withdrew from treatment will be summarized by primary reason for withdrawal and all reasons for withdrawal.

Participants who withdrew from treatment will be listed and the listing will include the number of days in the trial until withdrawal from treatment, the number of days since the last IMP, and the primary reason for withdrawal, and all reasons for withdrawal.

13.5.6 Efficacy Analysis

13.5.6.1 Continuous Efficacy Endpoints

In the eDiary, information regarding number of attacks, level of severity of pain of the attack(s) as well as use of abortive medication is gathered daily or weekly. When analysing data from the eDiary, three different data structures will be considered: weekly scores based on daily data, monthly scores based on weekly scores (regardless of the weekly scores originating from data being daily or weekly), and weekly scores based on either daily or weekly reported data covering all weeks which will be used descriptively to show the data over time (for further details see section [23.1](#)). The endpoints listed below are covered by applying the three different data structures in the MMRM as in section [13.5.1.2](#) using FAS and DPS3 with the relevant time variable, appropriate baseline value (for endpoints considering weekly/monthly attacks and integrated measure the log-transformed baseline

values will be used for all other endpoints there will be no transformation of the baseline values), and the appropriate contrast statement as well as a different list of covariance structures to get estimates of mean values, their standard errors (SEs) as well as two-sided 95% CIs:

- Change from Baseline in the weekly number of times an abortive therapy (oxygen and/or triptans) was used (Weeks 1-4, 13-16, 25-28, 37-40)
- Change from Baseline in the number of weekly attacks (Weeks 1-4, 13-16, 25-28, 37-40)
- Change from Baseline in the average attack related daily pain (including days with no attacks), as assessed using the 5-point self-rating pain severity scale (Weeks 1, 2, 3, 4, 13, 14, 15, 16, 25, 26, 27, 28, 37, 38, 39, 40)
- Change from Baseline in the number of monthly attacks (Months 1,2, ..., 12)
- Change from Baseline in the pain per attack assessed by the 5-point self-rating pain severity scale scores (Months 1,2, ..., 12)
- Change from Baseline in the monthly number of times an abortive therapy (oxygen and/or triptans) was used (Months 1,2, ..., 12)
- Change from Baseline in the weekly integrated measure of frequency and intensity of attack related pain, that is, the sum of the intensity (worst pain on a 5-point self-rating pain severity scale) for each attack during a week (Weeks 1, 2, 3, 4, 13, 14, 15, 16, 25, 26, 27, 28, 37, 38, 39, 40) or the intensity of attack related pain multiplied by the weekly number of attacks (Weeks 5, 6, ..., 12, 17, 18, ..., 24, 29, 30, ..., 36, 41, 42, ..., 48)

Continuous endpoints using weekly scores based on daily data will first use an unstructured covariance structure. If this analysis fails to converge the following covariance structures will be tried out:

- UN(15) - banded unstructured
- UN(14) - banded unstructured
- UN(13) - banded unstructured
- UN(12) - banded unstructured
- TOEPH – heterogenous Toeplitz
- CSH – heterogenous compound symmetry
- TOEP - Toeplitz
- CS - Compound Symmetry

and the one with the lowest AIC amongst the ones that converged will be applied.

Continuous endpoints using monthly scores will first use an unstructured covariance structure. If this analysis fails to converge the following covariance structures will be tried out:

- UN(11) - banded unstructured
- UN(10) - banded unstructured
- UN(9) - banded unstructured
- TOEPH – heterogenous Toeplitz
- CSH – heterogenous compound symmetry
- TOEP - Toeplitz

- CS - Compound Symmetry

and the one with the lowest AIC amongst the ones that converged will be applied.

Weekly scores based on daily or weekly reported data will try out the following list of covariance structures:

- CSH – heterogenous compound symmetry
- TOEP - Toeplitz
- CS - Compound Symmetry

and the one with the lowest AIC amongst the ones that converged will be applied.

In addition to estimates, SEs and CIs the following estimates will be calculated:

- Change from Baseline in the number of weekly attacks, the weekly pain per attack score, the average attack related daily pain, the weekly integrated measure of frequency and intensity of attack related pain, and the weekly number of times an abortive therapy was used for Weeks 1-2 and Weeks 1-4 using data type 1)
- Change from Baseline in the number of monthly attacks, the monthly pain per attack score, the monthly integrated measure of frequency and intensity of attack related pain, and the monthly number of times an abortive therapy was used for Months 1-3, Months 4-6, Months 7-9, Months 10-12, Months 1-6, Months 7-12 and Months 1-12 using data type 2)

Each SIS domain score, the EQ-5D-5L VAS and each WPAI:GH2.0 sub-score will be analysed using the MMRM from section [13.5.1.2](#) considering FAS with the relevant time variable and appropriate baseline value (not log-transformed) as well as the same approach for choice of covariance structure to be applied.

PGIC will be analysed using the MMRM from section [13.5.1.2](#) considering FAS with the relevant time variable and no baseline value as well as the same approach for choice of covariance structure to be applied.

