
Primary Objective
 
• To evaluate the long-term safety and tolerability of eptinezumab in patients with cCH	
• Endpoints for the primary objective:
– adverse events– absolute values and changes from baseline in clinical safety laboratory test values, vital signs, weight, and electrocardiogram (ECG) parameter values– potentially clinically significant (PCS) clinical safety laboratory test values, vital signs, weight changes, and ECG parameter values– development of specific anti-eptinezumab antibodies (ADA), including neutralizing antibodies (NAbs)– Columbia-Suicide Severity Rating Scale (C-SSRS) score

Secondary Objectives

- To evaluate the efficacy of eptinezumab in patients with cCH

- Endpoints for the secondary objective (efficacy):
 - Conversion from cCH to episodic cluster headache (Week 0 to Week 48): Number of patients with no cluster headache attacks for ≥ 3 consecutive months (≥ 13 consecutive weeks)
 - Change from baseline in weekly number of times an abortive therapy (oxygen and/or triptans) was used (calculated for each infusion with eptinezumab, taking the average across the first 4 weeks after the infusion)
 - Change from baseline in the average number of weekly attacks (calculated for each infusion with eptinezumab, taking the average across the first 4 weeks after the infusion)
 - Change from baseline in the 5-point self-rating pain severity scale (calculated for each infusion with eptinezumab, taking the average across the first 4 weeks after the infusion)
 - Response: $\geq 30\%$ reduction in number of weekly attacks (calculated for each infusion with eptinezumab, based on the average across the first 4 weeks after the infusion)
 - Response: $\geq 50\%$ reduction in number of weekly attacks (calculated for each infusion with eptinezumab, based on the average across the first 4 weeks after the infusion)
 - cCH remission (Week 0 to Week 48): Number of patients with no cluster headache attacks for ≥ 1 month (5 consecutive weeks)
 - cCH remission (Week 0 to Week 12): Number of patients with no cluster headache attacks for ≥ 1 month (5 consecutive weeks between the first and second infusion)
 - cCH remission (Week 12 to Week 24): Number of patients with no cluster headache attacks for ≥ 1 month (5 consecutive weeks between the second and third infusion)

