The statistical software used will be SAS®, Version 9.4 or later.

22 Changes to Analyses Specified in the Protocol

In the definition of FAS monthly has been changed to weekly to accommodate that there are endpoints considering weekly data.

There has been a clarification of the phrasing of the endpoints from the protocol. Furthermore, the names of the different types of endpoints have also been changed to describe these in a concise way.

The following endpoints have been added for completeness:

- Response: $\geq 75\%$ reduction from Baseline in the number of weekly attacks (Weeks 1-4, 13-16, 25-28, 37-40)
- Change from Baseline in the weekly integrated measure of frequency and intensity of pain, that is, the sum of the intensity (worst pain on a 5-point self-rating pain severity scale) for each attack during a week (Weeks 1, 2, 3, 4, 13, 14, 15, 16, 25, 26, 27, 28, 37, 38, 39, 40) or the intensity of pain multiplied by the weekly number of attacks (Weeks 5, 6, ..., 12, 17, 18, ..., 24, 29, 30, ..., 36, 41, 42, ..., 48)
- Use of triptans (Weeks 1-48)
- Use of oxygen (Weeks 1-48)
- Use of preventive medication (Weeks 1-48)
- Response: $\geq 75\%$ reduction from Baseline in the number of monthly attacks (Months 1,2, ..., 12)
- Sustained response: $\geq 75\%$ reduction from Baseline in the number of monthly attacks for any month, where all the subsequent Months also had $\geq 75\%$ reduction from Baseline in the number of monthly attacks (Month 1,2, ..., 12)
- A maximum score of mild in the 5-point self-rating pain severity scale (Months 1, 2, ..., 12)
- Change from Baseline in the number of weekly attacks (Weeks 1-4 and Weeks 1-2)
- Change from Baseline in the number of monthly attacks (Months 1-12)

The estimand part of the efficacy analyses were not included in the protocol. It has been added to the SAP for clarification.

The baseline score is log-transformed for MMRMs using number of weekly attacks, number of monthly attacks and weekly integrated measure of frequency and intensity of attack related pain.

23 Details on Data Handling

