23.2.1.3 Imputation of Missing Post-baseline eDiary Assessments

The strategy of imputation of missing values is given by:

1. For each weekly score in the periods with daily entries in the eDiary, prorating is used to impute any missing data when data have been observed for at least 4 days in a week, to have full weekly scores
2. For each monthly score, prorating is used to impute any missing data when data have been observed for at least 2 weeks in a month (after prorating weekly scores), to have full monthly scores

For a 7-day weekly period where the eDiary is completed in at least 4 out of 7 days, the number of attacks will be calculated using prorating:

$7 * (\text{Reported number of daily attacks/Reported eDiary Days})$

For participants where the eDiary is completed in 3 days or less, the 7-day weekly observation will be set to missing.

For a 4-week monthly period where the eDiary is completed in at least 2 out of 4 weeks, the number of attacks will be calculated using prorating:

$4 * (\text{Number of weekly attacks/Reported eDiary Weeks})$

For participants where the eDiary is completed in 1 week or less the 4-week monthly observation will be set to missing.

Use of abortive medication is prorated using the same criteria and formulas as above where *Reported number of daily attacks* is replaced by *Reported number of daily times an abortive medication was taken* and *Number of weekly attacks* is replaced by *Number of weekly times an abortive medication was taken*.

The severity of attacks is prorated using the same criteria as above using the same formulas as in section [23.2.1.2](#).

The derivation of the three pain scores can be seen in [Panel 5](#). When calculating the average attack related daily pain and the weekly integrated measure of frequency and intensity of attack related pain, a value of 0 will be added to the nominator and count as a day in the denominator for days/weeks with 0 attacks. Furthermore, the weekly pain per attack is not defined for days/weeks with 0 attacks.

Panel 5 Definitions of Post-Baseline Pain Scores

	Daily eDiary	Weekly eDiary
Average attack related daily pain	Sum of the average daily pain across days with data/number of days with data	NA
Weekly pain per attack	Sum of pain across attacks/number of attacks	Pain
Monthly pain per attack	Sum of the weekly pain per attack scores/ number of the weekly pain per attack scores	

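### For average attack-related daily pain, the SAP names a 4-week average with a CI only after the first infusion, although the protocol's pain endpoint asks for one after each of the four

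*SAP*

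**What the plan says.** Protocol section 2 (Panel 3), repeated in the synopsis, gives the secondary pain endpoint as "Change from baseline in the 5-point self-rating pain severity scale (calculated for each infusion with eptinezumab, taking the average across the first 4 weeks". The attack endpoint has the same form: "Change from baseline in the average number of weekly attacks (calculated for each infusion with eptinezumab, taking the average across the first 4 weeks". Abortive use is defined the same way, and the 30% and 50% response endpoints are based on the same 4-week average. With four infusions, each endpoint has four such results.

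SAP chapter 5 (Panel 2) restates all of these as single-week endpoints for the 16 weeks with a daily diary. In the list of modelled endpoints in SAP 13.5.6.1, attacks appear as "Change from Baseline in the number of weekly attacks (Weeks 1-4, 13-16, 25-28, 37-40" and abortive use as "was used (Weeks 1-4, 13-16, 25-28, 37-40", while average attack-related daily pain is written out as 16 separate weeks. Each listed endpoint is to get means, SEs and two-sided 95% CIs from the MMRM.

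The same section then names additional averaged estimates. For the 16-week data structure they are "for Weeks 1-2 and Weeks 1-4 using data type 1", and daily pain is in that list. For the monthly data structure there are averages across the whole trial, but daily pain is not among the variables.

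Panel 5 (SAP 23.2.1.3) defines average daily pain for daily-diary weeks as "Sum of the average daily pain across days with data/number of days with data". It marks the score not applicable for the weekly diary and has no monthly row for it. Chapter 22 describes the rewording of endpoints in one sentence: "There has been a clarification of the phrasing of the endpoints from the protocol".

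**The concern.** The averaging window is part of how the protocol defines this endpoint: "calculated for each infusion with eptinezumab, taking the average across the first 4 weeks after the infusion". If the SAP is followed as written, the pain endpoint gets that summary after infusion 1 and only single-week values after infusions 2, 3 and 4. In a 48-week trial the later infusions show whether an early change in pain is repeated, and the natural display is four per-infusion means with CIs side by side. For pain, the plan produces one of the four.

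The change is also hard to see. Chapter 22 itemises added endpoints but not the replacement of per-infusion averages by single weeks, so a reader comparing the report with the protocol would find three results missing without explanation.

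**Working it through.** **Inputs.** Four infusions, each followed by 4 weeks of daily diary (Protocol 3.1; SAP chapter 2). A month is 28 days (SAP 3.4). Score definitions are in SAP 23.2.1.2 and 23.2.1.3, and modelled endpoints in SAP 13.5.6.1.

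**Step 1: the plan's own count.** SAP 23.1 states 16 weekly scores for the first data structure: 4 infusions x 4 weeks = 16. This reproduces.

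**Step 2: do the monthly results fill the gap?** Using month = floor((week - 1)/4) + 1:
- Weeks 13-16: (13 - 1)/4 = 3 and floor((16 - 1)/4) = 3, so Month 4.
- Weeks 25-28: (25 - 1)/4 = 6 and floor((28 - 1)/4) = 6, so Month 7.
- Weeks 37-40: (37 - 1)/4 = 9 and floor((40 - 1)/4) = 9, so Month 10.

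The monthly count is 4 times the mean of the observed weeks, and the weekly baseline is the monthly baseline divided by 4. A change in monthly attacks divided by 4 is therefore a change in average weekly attacks, and the percentage reduction is the same on either scale.

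**Step 3: endpoint by endpoint.**

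| Protocol per-infusion endpoint | Single-week results | Weeks 1-4 | After infusions 2-4 |
|---|---|---|---|
| Weekly attacks | yes | named average | monthly model, Months 4, 7, 10 |
| Abortive use | yes | named average | monthly model, Months 4, 7, 10 |
| 30% and 50% response | yes | monthly response, Month 1 | monthly response, Months 4, 7, 10 |
| Pain (as average daily pain) | yes, 16 weeks with SE and CI | named average | none named |

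For daily pain this gives 4 x 3 = 12 single-week estimates after infusions 2 to 4, and 0 of 3 block averages.

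**Step 4: can a reader recover the missing result?** The point estimate, yes: the contrast is the mean of four reported least squares means. The SE, no, because it needs their covariances. With equal variances and a common correlation rho (both assumed; the documents give neither), the variance of a 4-week mean is the single-week variance times (4 + 12 rho)/16, so

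SE ratio to a single week = sqrt((1 + 3 rho)/4).

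- rho = 0: sqrt(1/4) = 0.50
- rho = 0.3: sqrt(1.9/4) = 0.69
- rho = 0.5: sqrt(2.5/4) = 0.79
- rho = 0.7: sqrt(3.1/4) = 0.88
- rho = 0.9: sqrt(3.7/4) = 0.96

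The range is too wide for a reader to guess the CI from the weekly SEs.

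**The case against.** The strongest reply is that the later infusions are well covered. Months 4, 7 and 10 carry attacks, abortive use and response. The long-term estimand in SAP 13.5.3 concerns monthly attacks over Months 1-12, and 13.5.6.1 adds averages by infusion cycle. This stands. A reader might infer that the SAP averages only after the first infusion for every endpoint, or that maintenance of effect goes unexamined; the documents support neither.

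A second reply is that daily pain is estimated after infusions 2 to 4, week by week with SEs and CIs. This also stands. It would be wrong to say that pain after those infusions is never estimated; what is absent is the 4-week average with its CI.

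A third reply is that the protocol names the 5-point scale, not daily pain, and leaves diary derivations to the SAP (Protocol 16.8.2), which also reports other pain summaries. The choice of daily pain is indeed the SAP's to make, but the per-infusion averaging is set by the protocol, and the alternatives do not replace it. Monthly pain per attack is exploratory, and its weekly component is undefined when there are no attacks, so attack-free weeks drop out; daily pain counts attack-free days as 0. The averages of the integrated measure by infusion cycle span 12 weeks and mix frequency with intensity.

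Finally, 13.5.6.1 allows whatever contrast is appropriate, which could be read to include these averages. It specifies none. Nor does block notation show that averaging is meant: chapter 22 writes the 75% weekly response in blocks where Panel 2 lists single weeks.

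**Conclusion.** The point holds for one endpoint. For average attack-related daily pain, three of the four protocol-specified 4-week averages have no named estimate with a CI, no monthly score supplies them, and chapter 22 does not declare the change.

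The consequence is modest. The primary endpoints are safety endpoints, there are no key secondary efficacy endpoints, and no formal testing is planned, so no decision rule depends on this. What is lost is a descriptive result that the protocol promised, and a clear record that it was changed. No particular gain in precision should be claimed: the SE ratios above rest on an assumed equal-variance, equal-correlation structure. The gap itself depends on no such assumption, only on taking SAP 13.5.6.1 and Panel 5 as written. The change is worth making because it costs almost nothing.

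**What to change.** In the planned 16-week MMRM for average attack-related daily pain, add three contrasts, with weeks ordered as in SAP 13.5.1.2:
- Weeks 13-16: positions 5 to 8, divisor 4
- Weeks 25-28: positions 9 to 12, divisor 4
- Weeks 37-40: positions 13 to 16, divisor 4

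Report them with Weeks 1-4 as the protocol's per-infusion pain endpoint, each with SE and 95% CI. In chapter 22, list the move from per-infusion averages to single weeks as a change.

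Adding the same contrasts for weekly attacks and abortive use is optional, because the monthly model already covers those blocks. It would keep them in the data structure that SAP 23.1 calls most valid for these weeks.

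The cost is three contrast lines, one sentence in the SAP and three more descriptive estimates to report. No new data or model is needed.
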